8.7.3.1 HbA1c

HbA1c is collected at week -7 to -4 (visit 1), baseline, week 12 (visit 11), and week 24 (visit 15). The measurements are performed by the central laboratory.

Actual values and changes from baseline at each time point will be computed and summarized by treatment group. Treatment difference and 95% confidence interval will be displayed along with p-values.

A sensitivity analysis for HbA1c will be performed using multiple imputation to impute missing values with non-missing subjects within the same treatment group using a pattern mixture model with the complete-case missing values (CCMV) method (Little 1993). After imputation, treatment difference, 95% CI, and p-values will be generated using same MMRM model as above. Sample imputation code is provided in Appendix 10.1.4.

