7.3 Secondary Endpoints

The following efficacy measures (both actual and change values) will be summarized at baseline and scheduled visit. A mixed model repeated measures (MMRM)-effects model will be performed for continuous variables without imputing missing values. The MMRM model will include the fixed, categorical effect of treatment group assignment, visit, treatment group-by-visit interaction and the other fixed effect terms Investigator, basal insulin dose time, and baseline value as covariates. Contrasts of LS mean at each scheduled visit will be used to evaluate all pairwise treatment comparisons, and 95% confidence intervals for treatment differences in LS means will be computed for each visit.

- Change in HbA1c from baseline.
- Change in fasting plasma glucose from baseline.
- Change in prandial, basal insulin and total daily insulin dose per unit body weight (U/kg) from baseline.
- Change in 7-point SMBG profile from baseline.

All above analyses will be performed on ITT set.

A sensitivity analysis for HbA1c will be performed using multiple imputation to impute missing values with non-missing subjects within same treatment group using pattern mixture model with the complete-case missing values (CCMV) method ([Little 1993](#)). After imputation, treatment difference, 95% CI, and p-values will be generated using same MMRM model as above.

The following safety measures (both actual and change values) will be summarized at baseline and scheduled visit. Similar MMRM model as efficacy analysis will be conducted for hypoglycemia rate. For antibody continuous variables, the MMRM model will include the fixed, categorical effect of treatment group assignment, visit, treatment group-by-visit interaction and the other fixed effect terms Investigator and baseline value as covariates. Contrasts of LS mean at each scheduled visit will be used to evaluate all pairwise treatment

comparisons, and 95% confidence intervals for treatment differences in LS means will be computed for each visit. For categorical data analyses, Fisher's exact test or Chi-squared test will be used.

The following analyses will also be performed and will form part of the totality of evidence to compare clinical efficacy and safety of two treatment groups:

- Incidence of ADA response and positive cross-reactive ADA; and incidence of positive NABs.

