8.7.3 Secondary endpoints

The following efficacy measures (both actual and change values) will be summarized at baseline and each scheduled visit.

- Change in HbA1c from baseline.
- Change in fasting plasma glucose from baseline.
- Change in prandial, basal insulin and total daily insulin dose per unit body weight (U/kg) from baseline.
- Change in 7-point self-monitored blood glucose (SMBG) profile from baseline.

A mixed model for repeated measures (MMRM) will be performed for continuous variables without imputing missing values. The MMRM model will include the fixed, categorical

effects of treatment group assignment, visit, treatment group-by-visit interaction, basal insulin dose time (AM/PM), and investigative site, as well as the baseline value as a continuous covariate.

The MMRM model results will be presented along with Least Squares (LS) means for the difference between the MYL1601-D and NovoLog[®] groups, standard errors, and two-sided 95% CIs for the difference between treatment groups. Contrasts of LS means at each scheduled visit will be used to evaluate all pairwise treatment comparisons, and 95% confidence intervals for treatment differences in LS means will be computed for each visit. The interaction of time points and treatment groups will also be presented. An unstructured covariance matrix will be assumed for within-subject error. The denominator degrees of freedom will be calculated according to the Kenward-Roger method.

In case of non-convergence of the above model using an unstructured covariance matrix, the following variance structures will be tested, and based on Akaike's information criteria the best fitting model will be chosen. The variance structures that will be considered for the within-subject variation in case of non-convergence are in this order: Heterogeneous Toeplitz, Toeplitz, and Compound Symmetry.

If convergence is still not obtained, the model may be revised to remove investigative site from the list of covariates.

All of the above analyses will be performed on the ITT set.

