proc mi data=outdata1 seed=24637883 nimpute=30  
out=outdata2;  
by treatment;  
monotone reg(hb11 hb15 / details);  
mnar model (hb11 hb15 / modelobs=ccmv(k=1));  
var hb0 hb11 hb15;  
run;
```

Step 4.

Reverse the process from Step 1, creating one record per subject visit, retaining the imputation number on each record.

Step 5.

Use code similar to what was used to analyze the primary efficacy endpoint, but run the code by `_imputation_`. For example,

```
/** step 5: Analyze the imputed datasets */  
proc sort data=imputed;  
by _imputation_ subjid avisitn;  
run;  
  
proc mixed data=imputed;  
by _imputation_;
```

```
class trt avisitn dosetime site;
model chg = trt avisitn dosetime site trt*avisitn base /
ddfm=kr s;
repeated avisitn / type=un;
lsmeans trt*avisitn / diff cl;
ods output ConvergenceStatus=converge;
ods output diffs=trtdiff;
run;
```

Convergence status is assessed by the condition that:

```
if pdg=1 and pdh=1 and status=0
```

in the dataset converge above, then model has converged. In the above code, if the model does not converge, replace the type=un option by each of the following: type=toeph, type=toep, and type=cs. You will also need to replace ddfm=kr with ddfm=bw. Choose the best fit model by checking the AIC and selecting the model with the lowest one. Please contact the statistician if this step is necessary.

Step 6.

Combine the 30 estimated statistics into one using PROC MIANALYZE.

```
data trtdiff;
set trtdiff (where=(avisitn=_avisitn));
run;

proc sort data=trtdiff;
by avisitn _imputation_;
run;

[figure not shown]
proc mianalyze data=trtdiff;
by avisitn;
modeleffects estimate ;
stderr stderr;
ods output parameterestimates=parms;
run;

proc print data=parms;
var avisitn estimate stderr lclmean uclmean probt;
run;
```

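### The one missing-data sensitivity analysis for HbA1c nearly reproduces the main MMRM, so agreement between the two is not evidence of robustness

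*SAP*

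**What the plan says.** SAP 8.7.3.1 sets the measurement times: "HbA1c is collected at week -7 to -4 (visit 1), baseline, week 12 (visit 11), and week 24 (visit 15"). Only Weeks 12 and 24 are post-baseline.

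The main analysis is in SAP 8.7.3: "A mixed model for repeated measures (MMRM) will be performed for continuous variables without imputing missing values". The same section adds: "An unstructured covariance matrix will be assumed for within-subject error". This is a likelihood analysis valid under missing at random (MAR).

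The missing-data check is same-arm CCMV multiple imputation, in SAP 8.7.3.1 ("A sensitivity analysis for HbA1c will be performed using multiple imputation to impute missing values with non-missing subjects within the same treatment group") and in matching words in Protocol 7.3 ("A sensitivity analysis for HbA1c will be performed using multiple imputation to impute missing values with non-missing subjects within same treatment group"). Of the step after imputation the SAP says: "After imputation, treatment difference, 95% CI, and p-values will be generated using same MMRM model as above". Appendix 10.1.4 codes the imputation in Step 3, by treatment, as "mnar model (hb11 hb15 / modelobs=ccmv(k=1"; no shift is applied.

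The retrieved-dropout imputation (SAP 7.2.1), the rule counting missing MYL-1601D subjects as TEAR positive (8.7.2.2) and the tipping-point analysis (8.7.2.3) are specified for TEAR, not for HbA1c.

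**The concern.** A missing-data sensitivity analysis should show what happens if the main analysis's assumption about unseen values is wrong. Here both analyses fill the gap at Week 24, in effect, from the relation seen in subjects of the same arm with complete HbA1c data, given baseline and Week 12. If subjects who leave MYL-1601D have worse control than that relation predicts, both analyses miss it in the same way and agree with each other.

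HbA1c is named in the totality of evidence used to interpret TEAR (SAP 2.1). Sites and subjects know the treatment (SAP 3.2.2), so dropout related to both arm and outcome is plausible. The risk is that near-certain agreement gets reported as robustness.

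**Working it through.** **The plan's own figure.** There is none to reproduce: the documents give no dropout rate, HbA1c SD or HbA1c margin, and Protocol 7.1 says that attrition is not considered.

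**Structure.** After Step 2 of Appendix 10.1.4 the data are monotone, so a subject with Week 24 also has Week 12.

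| Subject's pattern | Model needed | Donors under MAR | Donors under CCMV, k=1 |
|---|---|---|---|
| Week 24 missing | Week 24 given baseline and Week 12 | Same-arm subjects with both visits | The same subjects |
| Both missing | Week 12 given baseline | All same-arm subjects seen at Week 12 | Only those also seen at Week 24 |

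The two differ only in the Week 12 fill for subjects missing both visits. This needs no numerical assumption.

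**Size of a hidden shift.** Shift in the difference ≈ fraction of the MYL-1601D arm missing Week 24 × unseen worsening.
- Low end: 0.04 × 0.5% = 0.02%.
- High end: 0.20 × 1.0% = 0.20%.

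**Share missed.** In 2,000 simulated trials (250 per arm, 5% missing both visits, 7% missing Week 24 only, MYL-1601D dropouts worse by 0.8%; all assumed except the 250), the expected shift is 0.12 × 0.8% = 0.096%.
- Full data gave 0.0941, MAR 0.0252 and CCMV 0.0238.
- MAR missed (0.0941 − 0.0252)/0.0941 = 73%.
- CCMV missed (0.0941 − 0.0238)/0.0941 = 75%.
- MAR and CCMV differed by 0.0252 − 0.0238 = 0.0014% on average.

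Across the 4–20% and 0.5–1.0% range, the share missed was roughly 70–80% and the average MAR–CCMV gap about 0.004% or less.

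**Against a fitted MMRM.** Here the comparison is with the MMRM itself (treatment by visit, baseline, unstructured covariance; site and dose time left out). CCMV was run by arm with 30 imputations, in 60 trials per scenario. Assumed: baseline SD 0.9%, residual SD 0.6% at Week 12 and 0.5% at Week 24, monotone missingness. The worsening was added only to MYL-1601D values that are never observed.

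| Nominal dropout, test/reference | Worsening | Full data | MMRM | CCMV | Mean absolute gap | Largest gap |
|---|---|---|---|---|---|---|
| 10%/10% | 0.5 | 0.046 | −0.003 | −0.002 | 0.0029 | 0.0109 |
| 20%/20% | 0.5 | 0.108 | 0.014 | 0.015 | 0.0040 | 0.0124 |
| 20%/20% | 1.0 | 0.178 | −0.008 | −0.008 | 0.0038 | 0.0152 |
| 20%/20%, late dropout depends on Week 12 | 0.5 | 0.118 | 0.005 | 0.006 | 0.0093 | 0.0386 |
| 30%/10%, late dropout depends on Week 12 | 1.0 | 0.315 | 0.014 | 0.005 | 0.0107 | 0.0294 |

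Over all ten scenarios the mean gap was 0.0025–0.011%, against a standard error of about 0.057–0.062, and the correlation of the two estimates was 0.986–0.998. Because the worsening was wholly unseen here, both methods missed essentially all of it.

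**Stress scenario.** With 5–15% missing both visits and late dropout driven strongly by Week 12 HbA1c in the test arm only (18–36% of that arm missing Week 24), the mean gap rose to about 0.010–0.026% and the largest single gap to 0.063%. There CCMV moved in favour of the test arm, so it did not probe a worse outcome.

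**Does a real departure show?** Shifting the imputed test-arm values at 20% dropout gave 0.180 against a full-data 0.178 (worsening 1.0) and 0.107 against 0.108 (worsening 0.5).

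**The case against.** The strongest reply is that the plan limits the missing data. Subjects who stop treatment are asked to attend all remaining visits (Protocol 4.2.3 and 6.3.5), and early-termination HbA1c is mapped to the next planned HbA1c visit (SAP 8.1). Few subjects should then lack both visits, and those with complete HbA1c data can include some who are off treatment. This stands and lowers the importance: with 2% unobserved and a 0.8% worsening, the shift is only 0.02 × 0.8% = 0.016%. It does not make the check informative; fewer subjects missing both visits brings CCMV closer to MAR.

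It is also fair that HbA1c is secondary, that FPG and insulin dose are analysed too, and that keeping the tipping-point analysis for the primary endpoint is a defensible choice.

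Some stronger readings are tempting but not supported:
- **That the two analyses are identical.** They are not: CCMV uses by-arm regressions and treats subjects missing both visits differently, and single-trial gaps reached 0.039% in the main scenarios.
- **That MAR equates dropouts with completers.** It conditions on baseline and Week 12.
- **That the HbA1c result will be biased by a known amount.** Every size above rests on assumed dropout, SDs and worsening.
- **That no other HbA1c sensitivity analysis exists.** SAP 7.3 plans one that adds back the excluded site for major efficacy results, but it does not address missing values.
- **That the missing SUBJECT= term invalidates the analysis.** It is in sample code, and SAP 8.7.3 states the intended within-subject covariance.

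**Conclusion.** The point holds, at moderate importance. The structural result follows from two post-baseline visits and a monotone pattern, and needs no assumed numbers: for Week 24, CCMV with k=1 applies the MAR restriction. The only planned missing-data check on HbA1c therefore cannot show sensitivity to departures from MAR.

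The size is conditional on the assumptions: a shift of about 0.02–0.20%, of which both analyses miss roughly 70–80%, and more if none of the worsening shows in observed values. A reader might infer that the TEAR equivalence conclusion is at risk. The documents do not support that: HbA1c has no margin and enters only as supporting evidence.

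**What to change.** 1. Keep the CCMV run as supplementary and add a delta-adjusted analysis. Shift the imputed hb15 over a pre-stated grid in each arm, in both directions (for example 0 to 1.0%). Report the treatment difference and 95% CI at each shift. With no HbA1c margin, there is no tipping point to search for.
2. If there are at least 6 retrieved dropouts per arm, the retrieved-dropout imputation already defined for TEAR can also be applied. With 6 donors and three coefficients (intercept, baseline, Week 12), only 6 − 3 = 3 residual degrees of freedom remain, so this should not replace the grid.
3. Run the Step 2 MCMC in Appendix 10.1.4 by treatment. As coded it has no BY statement, so gaps before an observed Week 24 value are filled across arms, whereas the text says within arm.
4. As a minor code correction, add subject=usubjid to "repeated avisitn / type=un" in Step 5, so that the sample code matches SAP 8.7.3.

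The cost is additional imputation and model runs and one results table. No new data are needed.

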8.7.3.2 Fasting plasma glucose

The fasting plasma glucose is collected at week -7 to -4 (visit 1), baseline, week 4 (visit 9), week 8 (visit 10), week 12 (visit 11), week 16 (visit 12), week 20 (visit 13), and week 24 (visit 15, End of Treatment). The measurements are performed by the central laboratory.

Actual values and changes from baseline at each time point will be computed and summarized by treatment group.

A separate analysis will be performed excluding patients with no fasting status.

8.7.3.3 Daily insulin dose per unit body weight (mealtime, basal insulin and total) for days of 7-Point profiles

Patients will be asked to document the dose of insulin taken on the same day they will perform the 7-Point SMBG profiles (from week -2 to week 24). The measurements are taken the week prior to the visits, so the week prior to:

- Week -2 (Visit 4)
- Week 0 (Visit 6)
- Week 2 (Visit 8)
- Week 4 (Visit 9)
- Week 8 (Visit 10)
- Week 12 (Visit 11)
- Week 16 (Visit 12)
- Week 20 (Visit 13)
- Week 24 (Visit 15)

Doses will be recorded in the patient's diary. This data will be transcribed to the eCRF after the patient diary is collected, by the investigator or designee at scheduled visits. The patient should document the 3 pre-visit estimations in the diary; and will be advised to document any additional estimations.

There will be three doses variables: meal time insulin dose, basal insulin and total insulin dose.

Daily Meal time insulin dose: is the sum of all the total daily meal time insulin (Humalog) dose over the double-blind treatment period divided by the number of days measured. For the computation of total daily mealtime doses, only the patients with at least three mealtime doses at a particular day are considered. That is, total daily mealtime dose will not be computed for a day if the mealtime dose is recorded less than 3 times for that day.

Daily Basal insulin dose: is the average of the insulin dose over days measured during the double-blind period.

Daily Total insulin: is the sum of all total daily meal time doses and all basal insulin doses over the double-blind treatment period divided by the number of days measured. Similarly to total daily mealtime dose for which less than 3 mealtime doses are recorded, the missing insulin doses will not be considered for the average computation. That is, if either the mealtime doses are recorded less than 3 times or the basal insulin dose is missing for a particular day of collection, total insulin dose will not be computed. The total insulin dose will be computed for the remaining days where basal insulin dose and at least 3 mealtime doses are collected.

All doses will be divided by total body weight (kg) to convert to daily insulin dose (U) per unit body weight (kg). If body weight at that visit is missing, the weight from previous visit will be used.

8.7.3.4 7-Point Self-Monitored Blood Glucose (SMBG) profile

The 7-point SMBG profile recorded via glucometer and transferred by the subject to the diary, measurement will be performed by the subject at home on 3 days (of which 2 days are consecutive) in the week before the visit

The following summaries will be summarized at week 2, 4, 8, 12, 16, 20 and week 24:

Individual 7-Points SMBG:

The over 3-day averages will be performed for the measures taken at:

- Before breakfast
- Two hours after breakfast
- Before lunch
- Two hours after lunch
- Before dinner
- Two hours after dinner
- Just before sleep

Averages will be performed at each visit.

Excursions and averages in SMBG:

The following averages will be computed:

- Morning excursion
- Noon excursion
- Evening excursion
- Overall excursion
- Pre-meal average
- Post-meal average
- (4-point average) pre-meal and bedtime average
- Overall average

The individual excursion values will be obtained by subtracting post-meal values with pre-meal values, it will be applicable for morning excursion, noon excursion and evening excursion on the respective days. For the overall excursion at morning, afternoon and evening, the individual excursion values obtained on each day will be averaged across the three days.

To compute the overall excursion, first the average of the morning, noon and evening excursion within a day will be computed, then the average will be done across the 3 days.

The pre-meal average will be the average of the following timepoints: before breakfast, before lunch, before dinner on each day, then the average will be done over the 3 days.

The post-meal average will be the average of the following timepoints: two hours after breakfast, two hours after lunch, two hours after dinner on each day, then the average will be done over the 3 days.

The pre-meal and bedtime average will be the average of the following timepoints: before breakfast, before lunch, before dinner, just before sleep, then the average will be done over the 3 days.

The overall average will be the average of all the 7 timepoints during a day. The daily average will not be computed for a day if more than 3 timepoints are missing on a particular day. The overall average will be kept missing if the daily average is missing for all three days. If the average is missing for one or two days, the average of the remaining days will be considered for the computation.

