2.2 Background and Rationale

Insulin secretion in healthy subjects is characterized by relatively constant basal insulin secretion with a post-prandial surge. Type 1 diabetes mellitus (T1DM) is characterized by loss of the insulin-producing beta-cells of the islets of Langerhans in the pancreas, leading to a deficiency of insulin. The main cause of beta-cell loss is a T-cell mediated autoimmune attack ([de Graaff LC et al, 2007](#)). The principal treatment of patients with T1DM is initiation of insulin and diet control and careful monitoring of blood glucose levels.

The [Diabetes Control and Complications Trial](#) and other trials ([Reichard P et al, 1993](#)) provide conclusive evidence that maintaining tight glycemic control can prevent or delay microvascular and macrovascular complications in patients with T1DM. A number of different insulin regimens have been proposed for treatment of patients with T1DM. It is generally accepted that the so-called basal-bolus insulin regimen; 1 or 2 daily injections of long/intermediate-acting insulin covering basal insulin requirements in combination with 3 daily injections of short-/rapid acting insulin to cover meal-related insulin requirements, generally yields the best glycemic control in diabetes. Clear targets for plasma glucose levels have been recommended for basal-bolus insulin regimens ([American Diabetes Association 2019](#)).

Different insulin preparations are available for management of bolus insulin requirements, including; Apidra® (glulisine), Humalog® (lispro), NovoLog® (aspart). Rapid-acting insulin analogs have proven efficacy and offer good glucose control via regimen of 1 to 3 dose/injections per day. Insulin aspart is a rapid-acting insulin analogue administered once to three times a day to cover bolus insulin requirements per day.

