4.2 Inclusion and Exclusion Criteria

4.2.1 Inclusion Criteria

Subject eligibility should be reviewed and documented by an appropriately qualified member of the Investigator's study team before subjects are included in the study.

Subjects must meet all of the following inclusion criteria to be eligible for enrolment into the study:

1. Written and signed informed consent needs to be provided by subjects before starting any protocol-specific procedures.
2. Male and female subjects between the ages of 18 to 65 years, both ages inclusive.
3. Clinical diagnosis of type 1 diabetes mellitus for at least 6 months or more prior to screening.
4. Stable dose of once daily basal Lantus® or Toujeo® injection and multiple daily bolus NovoLog® or Humalog® injections for at least 3 months at screening.
5. Body mass index (BMI) of 18.5 to 35.0 kg/m² at screening (both values inclusive).
6. Stable weight, with no more than 5 kg gain or loss in the 3 months prior to screening (collected by subject interview during medical history).
7. Glycosylated hemoglobin (HbA1c) 6.5-10.0 % at screening.
8. Hemoglobin \geq 10.0 g/dL at screening.
9. Subject has the capability of communicating appropriately with the Investigator.
10. Subject is able and willing to comply with the requirements of the study protocol including the 7-point self-monitored blood glucose (SMBG), completion of subject diary records and following a recommended diet and exercise plan for the entire duration of the study.
11. Female subjects of childbearing potential who are willing to use oral contraception or acceptable methods of contraception, (e.g., intra-uterine device, spermicidal gel plus condom, diaphragm plus condom, etc.), from the time of screening and for the duration of the study, through study completion.
 - a. Periodic abstinence (e.g., calendar, ovulation, symptothermal, post-ovulation

methods) and withdrawal are not acceptable methods of contraception.

- b. Postmenopausal females must have had no regular menstrual bleeding for at least 1 year prior to screening.
- c. Female subjects who report surgical sterilization must have had the procedure at least 6 months prior to screening.
- d. All female subjects of childbearing potential must have negative pregnancy test results at screening and at clinic visits, as per the SCHEDULE OF ACTIVITIES (SOA).
- e. If female subjects have male partners who have undergone vasectomy, the vasectomy must have occurred more than 6 months prior to screening

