4.2 Secondary efficacy endpoint(s)

The secondary endpoint points are change from baseline to week 24 for the ITT population.

- Change in HbA1c from baseline
- Change in fasting plasma glucose from baseline
- Change in prandial, basal and total daily insulin dose per unit body weight (U/kg) from baseline
- Change in 7-point SMBG profile from baseline

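### SAP 8.7.3.3 defines insulin dose as a whole-period average, which contradicts the by-visit Week 24 endpoint, and its three-dose rule removes mealtime and total dose for eligible two-bolus subjects

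*SAP*

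**What the plan says.** SAP 8.7.3.3 (daily insulin dose per unit body weight) builds three variables from doses written in the diary on the SMBG profile days.

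- The mealtime variable "is the sum of all the total daily meal time insulin (Humalog) dose over the double-blind treatment period divided by the number of days measured".
- Basal dose "is the average of the insulin dose over days measured during the double-blind period".
- Total dose adds the two over the same period and divides by the number of days measured.

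A completeness rule applies to the first and third: "total daily mealtime dose will not be computed for a day if the mealtime dose is recorded less than 3 times for that day". Total dose is likewise not computed "if either the mealtime doses are recorded less than 3 times or the basal insulin dose is missing for a particular day of collection". Basal dose has no such rule.

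Other parts of the documents bear on these definitions:

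- SAP 4.2: "The secondary endpoint points are change from baseline to week 24 for the ITT population".
- SAP 8.7.3: actual and change values are summarised at baseline and each visit. The model is an MMRM with the baseline value as covariate, contrasts at each visit, and no imputation.
- SAP 8.8.5: one summary counts subjects who have visitwise TEAR, an HbA1c rise and a total-dose rise at a scheduled visit.
- SAP 3.1 and 3.3: the trial is open-label and the randomized mealtime insulin is MYL-1601D or NovoLog.
- Protocol 4.2.1, criterion 4: patients qualify on "multiple daily bolus NovoLog® or Humalog® injections for at least 3 months at screening". Protocol 2.2 describes insulin aspart as "administered once to three times a day".

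**The concern.** Two separate faults meet in one subsection. First, a single average over the treatment period has no value at Week 24 and no pre-randomization counterpart, so it cannot supply the endpoint or the model. Second, a day on which the patient took two boluses is a real day with a real dose, yet the rule treats it as missing.

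Insulin dose is a secondary endpoint. SAP 2.1 also names it in the totality of evidence around the primary objective, and total dose is one of the three criteria in the SAP 8.8.5 summary of possible antibody impact. A programmer following 8.7.3.3 to the letter would produce a different quantity from the one the rest of the SAP analyses.

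**Working it through.** The documents give no dose level, SD or share of two-bolus days, so there is no figure of the plan's own to reproduce for this endpoint.

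**1. Written definition against its uses**

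| Use | Needs | 8.7.3.3 gives |
|---|---|---|
| Change to Week 24 (SAP 4.2) | a Week 24 value and a baseline | one treatment-period mean |
| MMRM (SAP 8.7.3) | one value per visit, baseline covariate | one treatment-period mean |
| Combined summary (SAP 8.8.5) | total-dose rise at a scheduled visit | one treatment-period mean |
| Design (SAP 3.1, 3.3) | MYL-1601D or NovoLog, open-label | Humalog, double-blind |

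SAP 7.1 has a general baseline rule (last non-missing value before first randomized dose). It does not say whether, for insulin dose, that is one day or the mean of the profile days.

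**2. Weight of Week 24 under the literal reading**

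Inputs: 3 profile days per visit (schedule tables in both documents) and 7 post-baseline visits at Weeks 2, 4, 8, 12, 16, 20 and 24 (SAP 8.7.3.3).

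- Profile days: 7 × 3 = 21. Week 24 weight: 3/21 = 14.3%.
- Share of the Week 24 change that the mean keeps, under assumed time courses:
  - linear: (86/7)/24 = 51%
  - plateau from Week 4, 8 or 12: 93%, 82% or 74%
  - step after Week 16: 2/7 = 29%; step after Week 20: 1/7 = 14%

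**3. A subject who always takes two boluses**

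Every day has fewer than three recorded mealtime doses. Mealtime and total dose are therefore missing at all 7 post-baseline visits, and in the baseline profile if the pattern was the same then. With no imputation the subject leaves both models. Basal dose is still computed.

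**4. Level bias when a bolus was truly not taken**

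Assume three equal boluses on a full day, and basal equal to half of a full day's total.

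- Per-visit mean over 3 days, one bolus skipped: reported 3 per day, true 8/3, ratio 9/8 = +12.5% for mealtime dose. Total: 1/(0.5 + 0.5 × 8/9) = 1.059, or +5.9%.
- Per-visit mean, one bolus skipped on each of two days: 9/7 = +29% for mealtime dose.
- Literal mean over 21 days: one skipped gives 63/62 = +1.6%; one on each of two days gives 63/61 = +3.3%.
- In general, with a share q of true two-bolus days, mealtime dose is overstated by q/(3 − q) and total dose by q/(6 − q):

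| q (assumed) | Mealtime | Total |
|---|---|---|
| 5% | +1.7% | +0.8% |
| 10% | +3.4% | +1.7% |
| 20% | +7.1% | +3.4% |
| 30% | +11.1% | +5.3% |
| 50% | +20.0% | +9.1% |

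**5. The opposite case**

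If the third bolus was taken but not written down, dropping the day causes no bias in this calculation. Keeping it and counting the gap as zero would understate mealtime dose by q/3, which is 3.3% at q = 10%.

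**The case against.** The strongest reply is that a per-visit mean was plainly meant. SAP 4.2 and 8.7.3 require it, 8.7.3.3 lists the collection visits and uses body weight at the visit, and 8.8.5 works visit by visit. Humalog and double-blind look like leftover wording. This stands as evidence of intent. It does not repair the text, because 8.7.3.3 is where the variables are defined. The adjacent SMBG subsection states that averages are taken at each visit; the dose subsection does not.

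The second reply is that the rule turns on recorded doses, so it also screens incomplete diary days. That stands, and it means the rule cannot simply be removed.

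The third is that step 4 shows bias in level, while the endpoint is change compared between arms. If short days are equally frequent at baseline and on treatment, or in both arms, the bias may largely cancel. That stands too, and the documents give no reason to expect a difference between arms.

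The fourth is that Protocol 2.2 also describes three rapid-acting injections a day as the generally accepted basal-bolus regimen. Regular two-bolus patients may therefore be few. Their number is not given.

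**Conclusion.** The definition in SAP 8.7.3.3 is wrong as written and should be corrected. Taken literally it gives Week 24 a weight of 14.3%, defines no baseline dose in that section, and names an insulin and a design that do not belong to this trial. The three-dose rule also removes every mealtime and total dose value for a subject whom criterion 4 admits.

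The size of the effect on results is unknown. The +12.5% for one skipped bolus needs a per-visit mean, equal doses and a dose truly not taken; on the 21-day reading it is +1.6%.

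A reader might infer three stronger things that the documents do not support:

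- Two-bolus patients have no dose data at all. Basal dose is outside the rule.
- The retained doses, and so the treatment comparison, are biased upward. That holds for level only, only where doses were not taken, and no bias in the treatment difference has been shown.
- The Week 24 change is undefined, or a dose rise after antibody formation will be averaged away. SAP 4.2 and 8.7.3 define the change, and 8.8.5 looks for the rise at a scheduled visit. The fault is that 8.7.3.3 contradicts them.

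The primary TEAR analysis and the sample size are unaffected.

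**What to change.** Rewrite the derivation in SAP 8.7.3.3 as follows:

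- For each visit, define mealtime, basal and total dose as the mean over the profile days recorded in the week before that visit. Form baseline in the same way from the week before Visit 6.
- Keep a day on which a mealtime dose is documented as not taken, entering it as 0 U. Treat a day as incomplete only when a dose is unrecorded or its amount is missing.
- If the diary cannot separate these two cases, retain the three-dose rule and add a sensitivity analysis without it. The documents do not describe the diary's dose fields, so this needs checking first. Summing whatever is recorded is not a safe substitute, because it counts an unrecorded dose as zero.
- Replace Humalog with MYL-1601D or NovoLog, and delete the double-blind and whole-period wording.

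The cost is SAP wording and derivation code, plus one sensitivity analysis if the fallback is used. No new data are needed.
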